Amendment Date:

Axogen Corporation

Axoguard® Nerve Cap

PROTOCOL

A Multicenter, Prospective, Randomized and Subject Blinded Comparative Study of Axoguard® Nerve Cap and Neurectomy for the Treatment of Symptomatic Neuroma and Prevention of Recurrent End-Neuroma Pain

Protocol No. CAP-CP-001

CONFIDENTIAL - PROPRIETARY INFORMATION

Development Phase:	Pilot Cross-over to Comparative Parallel Group
Sponsor:	Axogen Corporation [name]
Sponsor Representative:	
Immediately Reportable Adverse Event:	Clinical Safety
V 3.0	
Issue Date:	27 Aug 2018

This clinical investigation will be performed to compliance with the protocol, the FDA Good Clinical Practices including 21 CFR part 50, 56, ICH E6, ISO 14155:2011 and local applicable regulatory requirements. This document is a confidential communication of Axogen, Corp. Acceptance of this document constitutes agreement by the recipient that no unpublished information contained herein shall be published or disclosed without prior written approval, except that this document may be disclosed to the appropriate Institutional Review Boards under the condition that they keep it confidential.

01 Mar 2021

Title of Study: A Multicenter, Prospective, Randomized, Subject Blinded Comparative Study of Axoguard[®] Nerve Cap and Neurectomy for the Treatment of Symptomatic Neuroma and Prevention of Recurrent End-Neuroma Pain

Estimated Number of Study Centers and Countries: Up to 20 Centers in the US

Study Type: Pilot to Comparative Parallel Group

Study Design: Randomized, controlled, prospective, subject blinded, multi-center, pilot to comparative parallel group study

Objective: The primary objective of the pilot phase of this study is to evaluate the difference in pain scores from baseline at 12 weeks; The primary objective of the comparative phase is the differences in pain assessments between the study groups at 12 months. The secondary objectives of this study are to compare degree of recovery over time (reduction in pain); quality of life and economic data for each treatment group over a 12-month period.

Study Population: Adult male and female subjects with symptomatic neuroma in the foot or ankle to at least one nerve where the nerve cannot be repaired to a distal nerve end

Test Product: Axoguard® Nerve Cap

Control: Neurectomy

Number of Subjects per Treatment Group: Enroll approximately 15 evaluable subjects in the pilot study. Enroll approximately 86 additional subjects for the randomized comparative study.

Duration of Study: Up to 13 months including screening period.

Inclusion Criteria:

Potential Subjects must:

- 1. Be able and willing to provide documented informed consent prior to the conduct of any study procedures;
- 2. Be an adult male or non-pregnant female ≥ 18 years of age;
- 3. Report baseline pain scores of >65mm on a 100mm Visual Analog Scale (VAS) at screening;
- 4. Have a documented diagnosis of symptomatic neuroma of at least one interdigital nerve in the foot which cannot be repaired to a distal nerve end;
- 5. Must have the of the following:
 - Pain with at least 3 of the following characteristics: burning, sharp, shooting, electric, parasthesias, numbness, cold intolerance;
 - Symptoms in a defined neural anatomic distribution
 - History of nerve injury or suspected nerve injury Must have at least 1:
 - Positive response to local anesthetic injection
 - US or MRI confirmation of neuroma
- 6. Be candidates indicated for surgery to address a symptomatic neuroma;
- 7. Have sufficient healthy soft tissue available to adequately cover the Axoguard® Nerve Cap;

- 8. In the surgeon's opinion, be likely to achieve complete resection of the symptomatic neuroma and be able to undergo implantation with the Axoguard[®] Nerve Cap or complete the neurotomy procedure in the control group;
- 9. Be willing and able to comply with all aspects of the treatment and evaluation schedule over a 12-month duration.

Exclusion Criteria:

Potential subjects must not:

- 1. Have undergone surgical treatment of pain from symptomatic neuroma in the target nerve(s)on three or more occasions;
- 2. Have biomechanical pathology and associated pain (such as plantar fasciitis, bursitis, sesamoid bone pain, tendinitis, etc);
- 3. Have a life expectancy of less than 12 months;
- 4. Have a history of or planned radiotherapy in the area of the end-neuroma;
- 5. be contraindicated for soft tissue implants.; this includes but is not limited to any pathology that would limit the blood supply; compromise healing or indicate the presence of a local infection;
- 6. Have a history of chronic ischemic conditions of the extremity;
- 7. Have a diagnosis of type 1 Diabetes Mellitus; or uncontrolled Type 2 Diabetes Mellitus (at the discretion of the investigator);
- 8. Have a history of diabetic neuropathy;
- 9. Be undergoing or expected to undergo treatment with chemotherapy, radiation therapy, or other known treatment which affects the growth of neural and/or vascular system;
- 10. Be immunosuppressed, immunocompromised or have planned immunosuppressive therapy within 12 months following the study procedure;
- 11. Have a History of congenital neuropathy or compressive neuropathy affecting the target limb;
- 12. Have a history of prior surgical management of more proximal compressive neuropathies or spinal conditions (e.g. spinal stenosis) not related to the symptomatic neuroma that affect the target limb;
- 13. Currently use or likely need to use medication during the study known to impact nerve regeneration or to cause peripheral neuropathy;
- 14. be pregnant or plan to become pregnant during the duration of the study;
- 15. Be or have been enrolled in another interventional study within 30 days prior to consenting;
- 16. Have a known allergy to anesthetic agents;
- 17. Have a known sensitivity to porcine derived materials; or
- 18. Be, in the opinion of the Investigator, unsuitable for inclusion in the study.

Conduct of Study: Randomized, controlled, prospective, subject blinded, multi-center comparative parallel group study. The study will be composed of eight (8) scheduled visits. See Appendix B: Schedule of Assessments for details.

Criteria for Evaluation:

Safety Endpoints

Primary Safety Endpoints:

- 1. Serious Adverse Events (SAEs) at 3 months
- 2. Adverse Events (AEs) or Unanticipated Adverse Device Effects (UADEs) at 3 months

Secondary Safety Endpoints:

1. SAEs, AEs and/or UADEs at 6, 9 and 12 months

Efficacy Endpoints

Primary Efficacy Endpoints:

- 1. Change in VAS score at 3 months compared to baseline (pilot study)
- 2. Change in VAS score at 12 months compared to baseline (comparative study)

Secondary Efficacy Endpoints:

- 1. Change in VAS score at 1, 3, 6, 9 and 12 months compared to baseline
- 2. Change in PROMIS score at 1, 3, 6, 9 and 12 months compared to baseline
- 3. Change Foot Health Status Questionnaire (FHSQ) score at 1, 3, 6, 9 and 12 months compared to baseline
- 4. Change in Quantity and class of pain medication use at 1, 3, 6, 9 and 12 months compared to baseline
- 5. Rate of recurrence of symptomatic neuroma

Statistical Methods:

All summaries of categorical data will be presented in frequencies and percentages. All summaries of continuous data will be presented by the number of non-missing values, mean, standard deviation, standard error, median, minimum, maximum, and coefficient of variation. Mann-Whitney U tests will be used to compare baseline data to ensure poolability across centers.

Sample Size and Analysis of Data:

The study is a randomized, controlled, prospective, subject blinded, multi-center study to evaluate the safety and performance of Axoguard® Nerve Cap for the treatment of symptomatic neuroma as compared to neurectomy. Tests of non-inferiority and superiority will be conducted in the comparative phase. Sample sizes for both pilot (15 subjects) and comparative (86 subjects) study phases were based on similar injury-type studies published and referenced in the protocol. As a point of reference, outcomes will also be compared to historical controls of subjects undergoing neurectomy.

Table of Contents

1. INTRODUCTION	5
1.1 BACKGROUND	5
1.2 Product Description	6
1.3 RISK ANALYSIS	8
1.3.1 Preclinical Testing for Axoguard® Nerve Cap	8

1. INTRODUCTION

1.1 Background

A neuroma is formed when a peripheral nerve's continuity is substantially disrupted or injured. Nerve trauma types include cut nerves as in amputations or autograft sites, crushed nerves in carpal tunnel syndrome, or stretched nerves from high velocity accidents. When a disrupted nerve cannot be repaired, Schwann cells, attempting to restore axonal continuity, proliferate ahead of the injury site. This process creates a path through which axons grow in a disorganized fashion. In severe tissue damage the regenerating axons cannot reach their target tissue, and instead form a tangled bulbous mass which causes pain when stimulated.^{2,3}

There is no currently accepted technique that has been clinically shown to prevent or mitigate neuroma formation. With more than 700,000 peripheral nerve injuries that require surgery every year and a rapidly increasing number of diabetes-related limb amputations, the number of patients suffering from debilitating neuroma pain is significant and increasing.⁴ Painful neuroma following amputation is a disabling condition for which treatments are not usually satisfactory.⁵

Currently available treatment options after limb amputation or an unrepaired transected nerve injury incompletely address pain-inducing neuroma formation.⁶ Treatments include both surgical methods to remove neuromas or limit neuroma pain with pharmacological therapies directed at pain management. Attempts to treat symptomatic neuroma formation have been met with limited success, which is reflected by the recorded use of over 150 physical and chemical treatment methods, none of which have been uniformly successful.^{7,8,9}

VAS pain scores have consistently been the measure of choice for assessing treatment interventions for pain, but the minimum clinically significant difference has typically been reported as a reduction between 14-20 mm. ^{11, 12}

Pharmacological methods may employ antidepressants, anticonvulsants, agonists, opioids, and lidocaine. Unfortunately, although pharmacological therapy may lead to transient relief, amputees often experience considerable side effects and reduced benefit over time, not to mention the possibility of abuse and dependency. Multiple clinical and non-clinical studies have demonstrated that neuroma pain is best controlled by the use of opioid medications, as it is refractory to other first-line neuropathic pain medications. For some amputees suffering from neuroma pain, the improvement in function offered by effective pain control is worth the trade-off of moderate to severe side effects including the risk of hyperalgesia. However, chronic use of opioid analgesics is associated with an increased risk of dependence and abuse. Local treatment options, such as cauterization and steroid, phenol, and alcohol injections are merely a temporary solution as repeated injections are required. Thus, a better approach to long-term relief may be surgical methods designed to prevent neuromas and eliminate or reduce symptomatic neuroma pain.

This study is to evaluate the safety and performance of the Axoguard Nerve Cap for surgical nerve amputation in the treatment of symptomatic neuroma compared to neurectomy. By providing a new treatment option to surgeons, the vision is for patients to benefit from reduced pain, improved rehabilitation outcomes, reduced dependence on opioids, and overall better quality of life. We predict that the partition design of the Axoguard Nerve Cap will cushion the axons within the nerve end and protect them from external stimulation and prevent painful neuroma formation post implant.

1.2 Product Description

Axoguard® Nerve Cap is a surgical implant that is a tubular device with one open end, one sealed end (cap) and internal channels designed to provide protection for a peripheral nerve end or stump where repair is unattainable or not desired. The device isolates the nerve stump from the surrounding soft tissue bed by pulling the nerve into the tube and suturing the nerve within the cap. The end of cap has a suturable tab to allow the surgeon to suture the device to surrounding tissue. See Figure 1.2-1 for Image of Axoguard® Nerve Cap, and figure 1.2-2 for Image of placement of Axoguard® Nerve Cap.

Axoguard[®] Nerve Cap is an extracellular matrix (ECM) that is fully remodeled during the healing process. When hydrated, Axoguard[®] Nerve Cap is easy to handle, soft, pliable, nonfriable and porous. Axoguard[®] Nerve Cap is flexible and pliable to accommodate movement of the joints and surrounding soft tissues and has sufficient mechanical strength to hold appropriately sized non-absorbable suture.

Processed porcine ECM is readily and available proven to be safe and effective in a wide range of clinical applications. 17, 18

Axoguard® Nerve Cap is provided sterile, for single use only, and in a variety of sizes to meet clinical needs. The device is supplied in a plastic tray within a sterile pouch. The pouch is heat-sealed to provide a sterile barrier and has a chevron seal. Contents of the package are guaranteed sterile unless the package is opened or damaged. Axoguard® Nerve Cap and packaging does not contain natural rubber latex. To assure patient safety, the small intestine submucosa (SIS) material undergoes a thorough disinfection, decellularization, and viral inactivation process. As a final step in the process, all SIS products are sterilized by validated sterilization methods. ²⁰

Porcine ECM processed by Cook Biotech is decelluarized and elicits an immune response that is predominately Th-2-like, promoting remodeling of soft tissues rather than eliciting an acute rejection response.²¹

Axoguard® Nerve Cap should be stored in a clean, dry location between $10-30^{\circ}\text{C}/50-86^{\circ}\text{F}$. The device should be used prior to the "Use By" date specified on the package. The "Use By" date is in the form Year-Month-Day. ¹⁹

Regulatory Classification: Axoguard[®] Nerve Cap is a class II device which obtained 510(k) clearance (K163446).²⁴

Figure 1.2-1: Image of Axoguard® Nerve Cap

[figure not shown]

Figure 1.2-2: Diagram placement of the Axoguard® Nerve Cap

1.3 Risk Analysis

Axoguard® Nerve Cap is contraindicated for use in any patient for whom soft tissue implants are contraindicated; this includes any pathology that would limit the blood supply and compromise healing or evidence of a current infection. Axoguard® Nerve Cap is derived from a porcine small intestinal submucosa (also called SIS) and should not be used for patients with known sensitivity to porcine derived materials.¹⁹

If any of the following conditions occur and cannot be resolved, careful removal of the device should be considered:

- Infection:
- Allergic reaction; and/or
- Acute or chronic inflammation (initial application of surgical graft materials may be associated with transient, mild, localized inflammation).

As with any surgical procedure, complications can occur such as pain, infection, decreased or increased nerve sensitivity, and complications associated with the use of anesthesia.

Additional complications that may be associated with these types of procedures may potentially occur after implantation. These complications may be expected and are not required to be recorded unless they increase in severity:

- mild incisional redness
- tenderness of surgical area
- mild edema of surgical area
- controllable pain at surgical area
- decreased sensation; and/or
- numbness

The following precautions should be taken into consideration prior to implanting the Axoguard® Nerve Cap: 19

Adverse events associated with the use of Axoguard® Nerve Cap may include but are not limited to:

[figure not shown]
- Failure to reduce symptomatic neuroma pain
- Transitory local irritation
- Infection
- Allergy
- Delayed wound healing; and/or
- Protrusion

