3.5 Study Endpoints

3.5.1 Safety Endpoints

Primary Safety Endpoint

- 1. The rate of occurrence of Serious Adverse Events (SAEs) at 3 months
- 2. The rate of occurrence of Adverse Experiences (AEs) or Unanticipated Adverse Device Effects at 3 months

Secondary Safety Endpoints

1. The rate of occurrence of SAEs, AEs and/or UADEs at 6, 9 and 12 months

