4. ADVERSE EVENTS

4.1 Adverse Event Definitions

An adverse event (AE) is defined as any untoward event (including abnormal lab findings) experienced by a subject (whether or not considered product-related by the Investigator or Sponsor) after the patient consents to participate in the trial. All AEs that occur during or after study product implantation/device insertion must be recorded in the subject's medical record and reported on the adverse event CRF.

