4.2 List of Anticipated Adverse Events

Consistent with the subject's informed consent form and the risk analysis section of this protocol, the following adverse events are known and may potentially occur during the subject's participation in this investigation:

- mild incisional redness;
- tenderness of surgical area;
- mild edema of surgical area;
- decreased pain at surgical area; and/or
- numbness

Severity of Adverse Events

Adverse events will be graded for severity and noted in the description of the event using the NCI (NIH)-developed Common Terminology Criteria for Adverse Events (NCI CTCAE), Version 5.0. In addition, any AE associated with subject termination from the study must be reported according to IRB requirements. The following severity grades (1-5) shown below in table 4-1 will be used in assessing adverse events using the CTCAE V5.0 as a guiding reference:

Table 4.3-1: Severity of Adverse Events

Grade	Description
Grade 1 (Mild)	Asymptomatic or mild symptoms; clinical diagnostic
98 9852 3	observations only; intervention not indicated

Grade 2 (Moderate)	Minimal, local or noninvasive intervention indicated; limiting age-appropriate instrumental ADL*
Grade 3 (Severe)	Medically significant but not immediately life-threatening; hospitalization or prolongation of hospitalization indicated; disabling; limiting self-care ADL**
Grade 4 (Life Threatening)	Life-threatening consequences; urgent intervention indicated
Grade 5 (Death)	Death related to AE

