4.5 Adverse Event Reporting Procedures

The Investigator is responsible for recording and reporting all Adverse Events observed or reported during the study, regardless of their relationship to the study product or their clinical significance. Subjects will be instructed to contact the site Investigator at any time if symptoms develop. The adverse event reporting window will begin at the time the subject signs the informed consent form and will continue throughout the study and up to 30 days following the End of Study visit. The Investigator is required to completely document all adverse events in detail in the subject's medical record (source documents) and report the event on the Adverse event CRF. Whenever possible, the AE will be

recorded using standard medical terminology in order to avoid the use of vague, ambiguous, or colloquial expressions.

Concurrent illnesses that are present at or before study device administration, which manifest with the same severity, frequency, or duration subsequent to study device administration, need not be recorded as AEs. Similarly, signs or symptoms related to a pre-existing disease (prior to patient consenting) need not be recorded as AEs and will be recorded in the medical history CRF. However, medical history events that increase in severity or duration must be reported on the AE CRF.

Each AE must be promptly recorded and sufficiently documented by the Investigator or a qualified designee, even if the AE is assessed by the Investigator as unrelated to therapy with study device. The Investigator or qualified designee should attempt, if possible, to establish a diagnosis based on the presenting signs and symptoms. Each AE must also be described by date and time of onset, date and time of cessation, frequency (intermittent or continuous), the action taken (change in study device, concomitant medication, etc.), and outcome. In addition, the site Investigator must evaluate all AEs with respect to their severity and relationship to the study device according to the definitions given in the above tables 4-1 and 4-2.

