9.3. Safety

9.3.1. Endpoints

The following measures will be collected and assessed for both the pilot and comparative studies.

Primary safety endpoints:

- 1. The rate of occurrence of SAEs at 3 months.
- 2. The rate or occurrence of AEs or UADEs at 3 months.

Secondary Safety Endpoints:

[figure not shown]
The rate of occurrence of SAEs, AEs and/or UADEs at 6, 9 and 12 months.

[figure not shown]

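### Protocol 1.3 exempts six new local post-operative events from recording unless they worsen, while Protocol 4.1, 4.5 and the SAP require every AE to be recorded, so the 3-month AE rate depends on which rule a site follows

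*Protocol*

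**What the plan says.** Protocol 1.3 introduces a list of six local events with the sentence "Additional complications that may be associated with these types of procedures may potentially occur after implantation". It continues: "These complications may be expected and are not required to be recorded unless they increase in severity". The six are mild redness at the incision, tenderness, mild edema, controllable pain, decreased sensation and numbness.

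The adverse event chapter gives a different rule. Protocol 4.1 states: "All AEs that occur during or after study product implantation/device insertion must be recorded". SAP section 6 repeats that sentence in its own AE definition. Protocol 4.5 gives the investigator this duty: "recording and reporting all Adverse Events observed or reported during the study, regardless of their relationship to the study product or their clinical significance". Its exceptions concern concurrent illnesses and signs or symptoms of pre-existing disease, and these must still be reported if they increase in severity or duration.

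Protocol 4.2 opens: "Consistent with the subject's informed consent form and the risk analysis section of this protocol, the following adverse events are known". It then lists four of the six exempt events (mild redness, tenderness, mild edema, numbness) as adverse events and gives no recording instruction.

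The affected endpoint is the second primary safety endpoint. Protocol 3.5.1 has "The rate of occurrence of Adverse Experiences (AEs) or Unanticipated Adverse Device Effects at 3 months"; SAP 9.3.1 has "The rate or occurrence of AEs or UADEs at 3 months". Neither sets the listed events aside.

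**The concern.** A coordinator who works from the AE chapter would record new mild redness two weeks after surgery as a Grade 1 event. A coordinator who relies on 1.3 would not. Both would be following the protocol, and the same patients would yield different 3-month AE rates.

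Two things are at stake. The first is the level of the rate: it cannot be interpreted, or compared across sites, without knowing which rule was used. The second is the comparison between arms. Under 1.3, local reactions that never worsen are not counted. Protocol 1.3 itself gives a reason why these could differ between a porcine graft and neurectomy alone: "initial application of surgical graft materials may be associated with transient, mild, localized inflammation". If such a difference exists, the exemption moves the observed AE difference toward zero.

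**Working it through.** **Step 1. Which rule governs?** The documents state no AE rate, so there is no figure of theirs to reproduce. The first check is textual.

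| Place | Rule for a new, non-worsening listed event |
|---|---|
| Protocol 1.3 | Need not be recorded |
| Protocol 4.1 | Must be recorded, no exception given |
| Protocol 4.5 | Must be recorded whatever its clinical significance; exceptions only for pre-existing or concurrent conditions |
| Protocol 4.2 | Calls four of the six adverse events; silent on recording |
| SAP section 6 | Same as Protocol 4.1 |
| SAP 9.3.1 and 9.3.2 | Endpoint and summaries cover all AEs; no exclusion |

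No place says which rule prevails. The severity table in Protocol chapter 4 includes a Grade 1 for asymptomatic or mild events needing no intervention, so that chapter expects mild events to be graded.

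**Step 2. Which events are in conflict?** Section 3.4.2 requires a baseline VAS of at least 65 mm and at least three pain characteristics from a list that includes numbness. Pain or numbness carried over from baseline is therefore often pre-existing, and 4.5 already exempts it unless it worsens. There 1.3 and 4.5 nearly agree. The conflict is confined to new events: redness, tenderness, edema, and new pain or sensory loss.

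**Step 3. Illustration of the level.** All inputs are assumed. Let o be the proportion of subjects with any other recorded AE, including worsened listed events. Let l be the proportion with a listed event that does not worsen. The two are taken as independent, and one rule is applied equally to both arms.

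- Rate under 1.3: o
- Rate under 4.1/4.5: 1 − (1 − o)(1 − l)
- Shift between rules: (1 − o) × l

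With o = 20%:

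| l | Under 1.3 | Under 4.1/4.5 | Half of subjects under each rule |
|---|---|---|---|
| 20% | 20% | 1 − 0.8 × 0.8 = 36% | (20 + 36)/2 = 28% |
| 40% | 20% | 1 − 0.8 × 0.6 = 52% | (20 + 52)/2 = 36% |
| 60% | 20% | 1 − 0.8 × 0.4 = 68% | (20 + 68)/2 = 44% |

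Over o = 10% to 30% and l = 20% to 60%, the shift runs from 0.7 × 0.2 = 14 points to 0.9 × 0.6 = 54 points.

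**Step 4. Illustration of the comparison.** Suppose listed events truly occur in 40% of cap subjects and 20% of neurectomy subjects, with o = 20% in both arms.

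- Under 4.1/4.5: 52% − 36% = 16 points.
- Half of subjects under each rule, none worsening: 36% − 28% = 8 points.
- Under 1.3, none worsening: 20% − 20% = 0 points.

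**Step 5. Sensitivity to worsening.** Protocol 1.3 does require a listed event to be recorded once it worsens. Here o counts only AEs other than the listed ones. If a quarter of listed events worsened (assumed), the recorded proportions under 1.3 would be 10% (cap) and 5% (neurectomy). The rates become 1 − 0.8 × 0.90 = 28% and 1 − 0.8 × 0.95 = 24%, a difference of 4 points rather than 0. In the largest case of Step 3 (o = 10%, listed events in 60%), the rate under 1.3 becomes 1 − 0.9 × 0.85 = 23.5% against 64%, so the shift falls from 54 to about 40 points.

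**The case against.** The best defense reads 1.3 as a specific exception to a general rule, with 4.2 tying the AE chapter to the risk analysis section. The text does not carry this. Section 4.5 sets out its own exceptions and expected post-operative events are not among them; 4.2 calls four of the six adverse events and does not repeat the exemption; 4.1 and the SAP never refer to it. The SAP does send the reader to the data management plan and CRFs for data-collection detail. Those are not available here and may state one rule, so inconsistent recording is possible rather than shown. That part stands.

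Other points also stand. SAP 9.3.2 plans summaries by seriousness, relatedness and severity plus individual listings, with no test. The safety clause of study success in Protocol 5.10 concerns product-related events, not the any-AE rate. Wound assessments at Week 2 and Month 1, pain assessments and diaries also capture the surgical site apart from AE entry. The illustration uses assumed rates throughout.

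A reader might infer three stronger claims, and the documents support none of them.

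- *Recording is biased by arm.* Surgeons are unblinded and 1.3 speaks of events after implantation, so differential recording is conceivable. Nothing shows that it happens or in which direction. One rule applied equally favors neither arm when there is no true difference.
- *The neurectomy arm falls outside the recording rules.* Section 1.3 refers to this type of procedure, 4.5 covers all AEs in the study, Protocol 5.9 compares AEs between arms, and SAP 7.4.4 includes neurectomy subjects in the safety population.
- *All pain and numbness is in dispute.* Baseline symptoms that do not worsen are already exempt under 4.5.

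**Conclusion.** The contradiction is real and stands in the current text. For new, non-worsening local events, Protocol 1.3 and Protocol 4.1/4.5 with SAP section 6 give opposite instructions, and the 3-month AE rate depends on which is followed. Following 1.3 also removes from the count the local reactions in which the arms could plausibly differ.

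The size cannot be derived from the documents. The figures above show only how the rate would move, given the assumed event proportions, independence and equal application in both arms. SAE and UADE counts are largely unaffected. This is a minor wording conflict about data collection that touches a primary safety endpoint; it does not undermine the trial and is worth correcting because the correction is cheap.

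**What to change.** **Protocol 4.5:** state one rule for both arms, for example: new or worsened redness, tenderness, edema, pain, decreased sensation and numbness at the surgical site are recorded as AEs with their CTCAE grade, in cap and neurectomy subjects alike. Symptoms unchanged from baseline stay under the existing pre-existing-condition exception.

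**Protocol 1.3:** delete the exemption sentence. The list of expected complications can remain.

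**SAP 9.3.2:** report the 3-month AE rate by treatment received for all AEs. As a sensitivity summary for data already collected, report it again excluding only listed local events that did not increase in severity. Worsened events must be kept, because both rules require them. Persistent or recurrent neuroma pain must also be kept, because 1.3 lists failure to relieve it as an adverse event of the device. Excluding the listed terms at every non-serious grade would be too broad for these reasons. In principle the narrower version is the same whichever rule a site followed, provided that worsening was recorded.

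**Cost:** a short protocol change with a notice to sites, one SAP sentence, slightly more AE entry and one extra table. The sensitivity version omits mild local reactions, which remain in the all-AE version to the extent that they were recorded.
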